4.7.2 Definition of End of Trial

The end of study will occur after the last patient has met off-study criteria and the data collection process is complete (time of study database lock).

5 SELECTION AND WITHDRAWAL OF PATIENTS

Inclusion and exclusion criteria are designed to properly define the target population for study participation and to identify those patients who may not be appropriate candidates for study participation based on specific co-morbidities or other clinicopathologic features of their disease. Patients must meet all the inclusion criteria; patients will be excluded from the study if they meet any exclusion criteria. No exceptions to these criteria will be granted by the Sponsor.

The patient population to be enrolled in this study will consist of adult patients with histologically-proven, unresectable locally advanced or metastatic melanoma, NSCLC, SCCHN tumors, urothelial cancer, or other cancers.

5.1 Inclusion Criteria

General:

1. Ability to provide informed consent and documentation of informed consent prior to initiation of any study-related tests or procedures that are not part of standard-of-care for the patient's disease. Patients must also be willing and able to comply with study procedures, including the acquisition of specified research specimens.
2. Age \geq 18 years old.
3. Dose Escalation Phase including Cohort 4: Histologically-proven unresectable locally advanced or metastatic:
 - a. Mesothelioma that has progressed during or following at least 1 and up to 3 prior systemic treatments for unresectable locally advanced or metastatic disease. The prior systemic chemotherapy must have included a pemetrexed (anti-folate)-based regimen in combination with platinum agent. For patients in whom pemetrexed was contraindicated or not tolerated or not an approved therapy (e.g., peritoneal mesothelioma), prior therapy with a first-line platinum-based regimen is required.
 - b. Urothelial cancer arising in the bladder, renal pelvis, ureter, or urethra that has progressed during or following at least 1 and up to 5 prior systemic treatments for unresectable locally advanced or metastatic disease (includes anti-PD-L1, anti-PD-1, but excludes other experimental therapies). Patients must have received at least one platinum-containing regimen (e.g., gemcitabine/cisplatin [GC], dose-dense methotrexate/vinblastine/doxorubicin/cisplatin [DDMVAC], or carboplatin/gemcitabine). No more than 5 prior systemic regimens allowed.
 - c. Thyroid cancer that has progressed during or following at least 1 and up to 5 prior chemotherapy regimen(s). Prior therapy excludes experimental therapies given in Phase 1 trials.

- d. Pancreatic cancer that has progressed during or following at least 1 and up to 3 prior chemotherapy regimens. Prior therapy excludes experimental therapies given in Phase 1 trials.
- e. Ovarian cancer that has progressed during or following at least 2 and up to 4 prior therapeutic regimens (e.g., 2 prior platinum containing regimens or if platinum resistant, a liposomal doxorubicin or topotecan containing regimen). Prior therapy excludes experimental therapies given in Phase 1 trials.
- f. Colon cancer that has progressed during or following at least 2 and up to 4 prior therapeutic regimens (e.g., fluoropyrimidine and/or irinotecan and/or oxaliplatin and/or anti-EGFR antibody containing regimens). Prior therapy excludes experimental therapies given in Phase 1 trials.
- g. Prostate cancer that has progressed during or following at least 1 and up to 5 prior therapeutic regimens (e.g., abiraterone, enzalutamide, docetaxel). Prior therapy excludes experimental therapies given in Phase 1 trials.
- h. Soft tissue sarcoma that has progressed during or following at least 1 and up to 5 prior therapeutic regimens. Prior therapy excludes experimental therapies given in Phase 1 trials.
- i. TNBC that has progressed during or following at least 1 and up to 5 prior therapeutic regimens. Prior therapy excludes experimental therapies given in Phase 1 trials.
- j. ccRCC that has progressed during or following at least 1 and up to 5 prior therapeutic regimens. Prior therapy excludes experimental therapies given in Phase 1 trials.
- k. Melanoma that has progressed during or following 1 or up to 5 prior systemic treatments for unresectable locally advanced or metastatic disease, with no more than 5 prior systemic regimens (excludes experimental therapies) allowed. Patients who are intolerant of, or have refused treatment with standard cancer therapy, will be allowed to enroll.
- l. SCCHN that has progressed during or following 1 or up to 5 prior systemic treatments for metastatic or recurrent disease deemed to be incurable by the investigator (patients who refuse radical resection for recurrent disease are eligible) with no more than 5 prior systemic regimens (excludes experimental therapies) allowed. Patients who are intolerant of, or have refused treatment with standard cancer therapy, will be allowed to enroll. Patients with upper esophageal or salivary gland tumors will not be considered as SCCHN.
- m. NSCLC that has progressed during or following 1 or up to 5 prior systemic therapies for unresectable locally advanced or metastatic

disease. Patients who are intolerant of, or have refused treatment with standard cancer therapy, will be allowed to enroll. Patients must not have had more than 5 prior systemic regimens (excludes experimental therapies) for unresectable locally advanced or metastatic disease.

- i. For patients with squamous cell carcinoma, or adenocarcinoma without known activating mutation: the prior systemic therapy is at least one platinum analogue based therapy with or without a docetaxel or pemetrexed containing regimen.
- ii. For patients with adenocarcinoma having a previously known activating driver mutation such as an epidermal growth factor receptor (EGFR) mutation or anaplastic lymphoma kinase (ALK) fusion: the prior systemic therapy is at least one TKI directed against the driver mutation.
- iii. Maintenance therapy following first-line therapy will not be considered a separate regimen of therapy.
- iv. Prior neoadjuvant chemotherapy for operable disease, adjuvant chemotherapy for completely resected disease or definitive chemoradiation therapy given for locally advanced disease will not be considered a separate regimen of therapy.

Cohort Expansion Phase: Histologically-proven unresectable locally advanced or metastatic:

- Melanoma that has progressed on or after at least one anti-PD-L1 or anti-PD-1 containing therapy. Patients in this cohort can have their PD-L1 tumor expression levels determined before or after enrollment.
- SCCHN, consisting of metastatic or recurrent disease (patients who refuse radical resection for recurrent disease are eligible); evaluated in 2 distinct cohorts, of up to 20 patients each where patients have progressed during or following:

SCCHN Cohort 1: a first line, platinum-based systemic therapy without receiving prior anti-PD-1 or anti-PD-L1 containing therapy or

SCCHN Cohort 2: a first-line, platinum-based systemic therapy and an anti-PD-1 or anti-PD-L1 containing therapy.

In each of the 2 cohorts, at least 10 of the enrolled patients will be human papilloma virus (HPV) positive (HPV positivity is determined as per local institutional standards, e.g., p16 detection by immunohistochemistry [IHC], or HPV *in-situ* hybridization [ISH]). Patients in both SCCHN cohorts can have their PD-L1 tumor expression levels determined before or after enrollment.

- NSCLC consisting of patients with unresectable locally advanced or metastatic disease that will be evaluated in 2 distinct cohorts of up to 20 patients each where patients have progressed during or following:
 - NSCLC Cohort 1: a first-line systemic therapy as outlined below (i-iv, based on tumor histology) without receiving prior anti-PD-1 or anti-PD-L1 containing therapy. These patients must have PD-L1 tumor expression determined by IHC analysis at levels accepted by the Sponsor prior to enrollment (< 1% tumor positivity score [TPS]).
 - NSCLC Cohort 2: a first line systemic therapy as outlined below (i-iv, based on tumor histology) and an anti-PD-1 or anti-PD-L1 containing therapy. Patients in this cohort can have the PD-L1 tumor expression levels determined before or after enrollment.
 - i. For patients with squamous cell carcinoma, or adenocarcinoma without known activating mutation: the prior systemic therapy is a platinum analogue based therapy with or without a docetaxel or pemetrexed containing regimen.
 - ii. For patients with adenocarcinoma having a previously known activating driver mutation such as an epidermal growth factor receptor (EGFR) mutation or anaplastic lymphoma kinase (ALK) fusion: the prior systemic therapy is a TKI directed against the driver mutation.
 - iii. Maintenance therapy following first-line therapy will not be considered a separate regimen of therapy.
 - iv. Prior neoadjuvant chemotherapy for operable disease, adjuvant chemotherapy for completely resected disease or definitive chemoradiation therapy given for locally advanced disease will not be considered a separate regimen of therapy.
- Urothelial cancer consisting of transitional cell or mixed transitional/nontransitional (predominantly transitional) cell cancer of the renal pelvis, ureter, bladder, or urethra, in a cohort of up to 16 patients. Patients must have received at least one platinum-containing regimen, either as neo-adjuvant, adjuvant, or for metastatic disease, and progressed on an anti-PD-L1 or anti-PD-1 containing therapy. Patients in this cohort can have the PD-L1 tumor expression levels determined before or after enrollment.
- 4. Eastern Cooperative Oncology Group (ECOG) performance status of 0 or 1 ([Appendix 4](#)).
- 5. Life expectancy \geq 12 weeks.

6. Measurable disease as per RECIST 1.1 criteria ([Appendix 5](#)) and documented by computed tomography (CT) and/or magnetic resonance imaging (MRI). Patients must have measurable disease to be enrolled on this study. Note: Lesions to be used as measurable disease for the purpose of response assessment must either a) not reside in a field that has been subjected to prior radiotherapy, b) have demonstrated clear evidence of radiographic progression since the completion of prior radiotherapy and prior to study enrollment.
7. Prospective determination of B7-H3 expression is not required to define eligibility for this study; however, tumor expression of B7-H3 will still be evaluated for all patients enrolled on the study, so patients must have sufficient tissue/slides for B7-H3 testing identified in order to be eligible. Patients should have a FFPE tumor specimen or unstained slides identified for analysis, to enable determination of the expression of B7-H3 within tumor specimens using IHC staining. If an archived tumor specimen is not available, patients who undergo a fresh tumor biopsy ([Section 7.11.4.3](#)) can have B7-H3 expression evaluated from an FFPE sample obtained from the tumor biopsy. In this case, the biopsy should be obtained prior to initiating study therapy. In cases in which an archived sample and fresh tumor sample are both available, B7-H3 expression can be confirmed with either FFPE sample.
8. All patients in the Expansion Phase will have the PD-L1 tumor expression levels assessed using an IHC method deemed acceptable by the Sponsor and based either on archival or new tissue biopsy samples, submitted as FFPE tissue samples.
 - a. Note: Patients in the NSCLC cohort who have not received prior anti-PD-1 or anti-PD-L1 therapy will need to have the PD-L1 IHC expression levels determined **prior to enrollment to determine eligibility**. All other patients can have PD-L1 tumor expressions determined prior to or after enrollment.
9. Patients enrolling in the study without prior documented PD-L1 tumor expression levels (determined by a Sponsor-approved method) should have a formalin-fixed, paraffin-embedded tumor specimen or unstained slides identified and available for analysis, to assess PD-L1 tumor expression levels, determined by a method selected by the Sponsor.

Laboratory Features:

10. Acceptable laboratory parameters as follows:
 - a. Platelet count $\geq 100 \times 10^3/\mu\text{L}$ without transfusion within 28 days prior to the initiation of study drug.
 - b. Absolute neutrophil count $\geq 1.5 \times 10^3/\mu\text{L}$ in the absence of any growth factor support within 28 days prior to the initiation of study drug.
 - c. ALT/AST $\leq 3.0 \times \text{ULN}$; for patients with hepatic metastases, ALT and AST $\leq 5 \times \text{ULN}$.

- d. Total bilirubin $\leq 1.5 \times$ ULN, except patients with Gilbert's syndrome, who may enroll if the conjugated bilirubin is within normal limits.
- e. Creatinine < 2 mg/dL, or a calculated or measured creatinine clearance > 50 mL/min.

Reproductive Features:

- 11. Female patients of childbearing potential (not surgically sterilized and between menarche and 1 year postmenopause) must have a negative urine pregnancy test performed within 72 hours prior to the initiation of study drug administration. Further, female patients of childbearing potential must agree to either remain abstinent or use acceptable contraceptive measures from the time of consent through 120 days after discontinuation of study drug administration. For female patients, two forms of contraception must be utilized and may include oral, transdermal, injectable or implantable contraceptives, intrauterine device (IUD), female condom, diaphragm with spermicide, cervical cap, use of a condom by the sexual partner or a sterile sexual partner. Periodic abstinence (e.g., calendar, ovulation, symptothermal and postovulation methods) and withdrawal are not considered acceptable forms of contraception in this study.
- 12. Male patients with partners of childbearing potential must use barrier contraception. In addition, male patients should also have their partners use another method of contraception from the time of consent through 120 days after discontinuation of study drug administration.
- 13. Female patients must not be breast-feeding.

Tumor Biopsy

- 14. Patients in the Cohort Expansion Phase who have one lesion considered to be potentially amenable to biopsy have the option of providing consent for paired pre-treatment and on-treatment biopsy samples. Tumor lesions used for biopsy should not be lesions used as RECIST target lesions, unless there are no other lesions suitable for biopsy. If a RECIST target lesion is used for biopsy, the lesion must be ≥ 2 cm in longest diameter. Tumor biopsies should be obtained only from lesions that are felt to be accessible with acceptable clinical risk, in the judgment of the investigator.

Previous Checkpoint Inhibitor Therapy

- 15. Patients who have previously received an immune checkpoint inhibitor (e.g., anti-PD-L1, anti-PD-1 anti-CTLA-4) prior to enrollment must have toxicities related to the checkpoint inhibitor resolved to \leq Grade 1 or baseline (prior to the checkpoint inhibitor) to be eligible for enrollment.

This excludes patients who experienced the following immune checkpoint inhibitor-related AEs (i.e., the following AEs make the patient ineligible despite the AE resolving to \leq Grade 1 or baseline):

- a. \geq Grade 3 ocular AE.
- b. Changes in liver function tests that met the criteria for Hy's Law ($> 3 \times$ ULN of either ALT/AST with concurrent $>2 \times$ ULN of total bilirubin and without alternate etiology).
- c. \geq Grade 3 neurologic toxicity.
- d. \geq Grade 3 colitis.

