4.2.3 Hepatic Non-Hematologic Dose Limiting Toxicity

- AST or ALT $> 5 \times$ ULN or total bilirubin $> 3 \times$ ULN
 - For patients with liver metastasis who begin treatment with Grade 2 AST or ALT, if the AST or ALT increases by $\geq 50\%$, relative to baseline and lasts for at least 1 week.
 - Please see **Section 6.5.2.2** for further management guidelines.
- Any event meeting the criteria for Hy's law as follows (all three features):
 - Aspartate aminotransferase (AST) and/or alanine aminotransferase (ALT) $> 3 \times$ ULN.
 - Concurrent elevation of total bilirubin $> 2 \times$ ULN without initial evidence of cholestasis.
 - No alternative etiology can be identified.

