4.5.1 Dose Delays

Patients who experience toxicity that is potentially dose-limiting should have study drug held pending assessment, management and resolution of the toxicity. For patients in whom the toxicity is assessed to be unrelated to study drug or for whom the toxicity does not meet the criteria for DLT, therapy may be re-instituted at the same dose and schedule that was administered prior to the event, presuming the toxicity has resolved to \leq Grade 1 in severity. Reinstitution of therapy shall be conducted as follows:

For patients in whom the toxicity is assessed to be related to study drug, dose interruptions of up to 14 days are allowed for drug related toxicity. This may include up to one missed dose of pembrolizumab and up to 2 consecutively missed doses of MGA271. For the MGA271+MGA012 combination, Cohort 4, this would allow for a maximum of one dose each of MGA271 and MGA012. The procedures at the original scheduled missed visit should be performed as soon as possible with treatment reinstated as if no delay had occurred, picking up at the day where the interruption occurred, and patients receive the full complement of pembrolizumab and MGA271 or MGA271+MGA012 or as outlined in The Time and Event Schedule ([Appendix 1](#)). Patients with infusion delays $>$ 14 days due to drug related toxicity will discontinue both study drugs, complete the End of Treatment visit, and then enter the Efficacy Follow-up Period.

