6.5.2.2.2 Elevations in Total Bilirubin

Management guidelines for patients experiencing elevations in total bilirubin are as follows:

Grade 1 elevations

- No specific therapy required

Grade 2 elevations

- Hold MGA271 and pembrolizumab or MGA012, until improvement to \leq Grade 1
- Consider oral steroids
- If improvement to \leq Grade 1 does not occur within 14 days, discontinue MGA271 and pembrolizumab or MGA012, and begin oral steroids

Grade 3 elevations

- For elevations in total bilirubin $> 3 \times$ ULN, permanently discontinue MGA271 and pembrolizumab or MGA012, and
- Initiate IV steroids; suggest methylprednisolone at a dosage of 2 mg/kg/day divided twice daily.
- If no response to corticosteroid therapy within 3 to 5 days is observed, consider adding immune suppression therapy with mycophenolate. Infliximab is not recommended because of a potential for autoimmune hepatitis (30).
- Monitor liver function testing at least twice weekly (or more frequently as clinically appropriate in the judgment of the investigator) until transaminases have returned to Grade 1 or baseline.

Grade 4 elevations

- Discontinue pembrolizumab or MGA012, and MGA271
- Treat as for Grade 3 elevation

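### Patients admitted under the Gilbert's exception can return to their own baseline bilirubin after a Grade 2 hold and still fail the release test in Protocol 6.5.2.2.2

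*Protocol*

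**What the plan says.** **Entry.** Protocol 5.1, criterion 10d, requires total bilirubin of at most 1.5x ULN, "except patients with Gilbert's syndrome, who may enroll if the conjugated bilirubin is within normal limits". The synopsis repeats this. Gilbert's syndrome is mentioned nowhere else, including the DLT, dose-delay and hepatic management sections.

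**Hold and release for Grade 2 bilirubin (6.5.2.2.2).** The instruction is "Hold MGA271 and pembrolizumab or MGA012, until improvement to" Grade 1 or lower. If that improvement "does not occur within 14 days, discontinue MGA271 and pembrolizumab or MGA012, and begin oral steroids".

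**Above 3x ULN (6.5.2.2.2, Grade 3).** Both drugs are stopped permanently. Total bilirubin above 3x ULN is also a DLT criterion in 4.2.3.

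**General dose delays (4.5.1).** "Patients who experience toxicity that is potentially dose-limiting should have study drug held pending assessment, management and resolution of the toxicity". If the event is judged unrelated, or is not a DLT, "therapy may be re-instituted at the same dose and schedule that was administered prior to the event, presuming the toxicity has resolved to" Grade 1 or lower. The time limit in that section covers drug-related delays only: delays of more than "14 days due to drug related toxicity will discontinue both study drugs".

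**Baseline wording elsewhere.** Criterion 15 lets earlier checkpoint-inhibitor toxicity count as resolved at "Grade 1 or baseline (prior to the checkpoint inhibitor) to be eligible for enrollment". The monitoring lines in 6.5.2.2 also accept Grade 1 or baseline, but only for transaminases.

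**The concern.** The protocol deliberately admits a group whose normal state may already exceed Grade 1 for total bilirubin, then releases a bilirubin hold only at Grade 1 or lower. Such a patient could have a rise, be held, return fully to the level at which enrolment was allowed, and still not qualify to resume. At 14 days the written instruction is to stop both drugs and begin oral steroids. Section 6.8 asks for corticosteroid use to be kept low because the study drugs act through T cells. At stake are loss of therapy and unneeded steroid exposure for an individual patient, and different handling of similar patients at different sites. The primary objectives and planned analyses are not at stake.

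**Working it through.** The plan gives no figure to reproduce. The check traces the rules, with simple arithmetic to show the width of the gap.

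**Inputs from the documents**
- Entry limit without the exception: 1.5x ULN (5.1, 10d). Anyone who needs the exception is above it.
- Grade 2 release test: Grade 1 or lower (6.5.2.2.2).
- Upper edge of the Grade 2 route: 3x ULN, above which the Grade 3 line applies (6.5.2.2.2).
- Grading scale: CTCAE v4.03 (6.5.2).

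**Assumptions**
- The Grade 1 ceiling for bilirubin is not printed. I take 1.5x to 2x ULN.
- Illustrative usual levels: 2.0x, 2.5x and 2.8x ULN.

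**Step 1. What starts the problem.** An unchanged baseline value triggers nothing. Under 7.8.6 a laboratory value becomes an AE only if it is a clinically significant abnormal change from baseline, and 6.5.2 addresses treatment-related toxicity. An on-treatment rise that leads to a hold is needed.

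**Step 2. How far below baseline the patient must fall to be released.** Required fall = 1 - ceiling / baseline.

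**Step 3. Which rises stay on the Grade 2 route.** Largest rise = 3 / baseline - 1.

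| Usual level (x ULN) | Required fall, ceiling 1.5x | Required fall, ceiling 2x | Largest rise staying at or below 3x ULN |
|---|---|---|---|
| 2.0 | 1 - 1.5/2.0 = 25% | 1 - 2.0/2.0 = 0% | 3/2.0 - 1 = 50% |
| 2.5 | 1 - 1.5/2.5 = 40% | 1 - 2.0/2.5 = 20% | 3/2.5 - 1 = 20% |
| 2.8 | 1 - 1.5/2.8 = 46.4% | 1 - 2.0/2.8 = 28.6% | 3/2.8 - 1 = 7.1% |

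With a 1.5x ceiling, every patient who needs the exception fails on return to baseline. With a 2x ceiling, only those whose usual level exceeds 2x fail, and at exactly 2.0x the rule works as written. The gap exists at both ends of the assumed range and only its width changes. The last column shows that the Grade 2 route narrows as the baseline approaches 3x ULN.

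**Step 4. Comparison with the neighbouring exception.** Criterion 10c admits patients with hepatic metastases and AST/ALT up to 5x ULN. For those who start with Grade 2 values, 4.2.3 and the Grade 3 line of 6.5.2.2.1 use a rise relative to baseline. Exception 10d has no such counterpart. The parallel is partial, because the Grade 2 transaminase hold also names only Grade 1.

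**Step 5. Exposure.** Section 2.3.1.1.2 reports the pembrolizumab cohorts closed with treatment complete. That leaves mainly Cohort 4, up to 15 dose-evaluable patients, of whom Gilbert's patients would be an unstated fraction.

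**The case against.** The strongest objection concerns 4.5.1. That section asks whether the toxicity has resolved, not whether the laboratory value has. At the patient's own baseline there is no abnormal change in the sense of 7.8.6, and the same section defines resolution as return to pre-treatment status, although in a paragraph on SAE follow-up. On that reading 4.5.1 already permits restart at baseline. This is reasonable, and it is why I call 4.5.1 ambiguous rather than defective.

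A reader might infer more: that a rise past 3x ULN judged unrelated leaves the patient neither stopped nor released, because the 14-day stop covers drug-related delays only. The documents do not support that. Section 4.5.1 can be read as just described, and the Grade 3 bilirubin line directs permanent discontinuation for rises managed under it. The note in 4.4 also allows therapy to be extended case by case with the Sponsor for a patient who is benefiting. Related rises above 3x ULN are therefore outside this point.

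The Grade 2 route is also narrow. A patient already at Grade 2 who rises within that grade may not count as having an increase in severity under the treatment-emergent definition (7.8.2.4). The hold then depends on the investigator judging the change clinically significant and treatment-related, and caution is defensible there. Section 6.5.2 calls its content general guidelines. All of this lowers the frequency, but none of it supplies a release criterion at baseline in 6.5.2.2.2.

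On size, a reader might reason from 2.3.3.1.2, where bilirubin increase was among the TEAEs seen in at least 20% of patients at MGA012 500 mg every 4 weeks. That is the same average daily dose as in Cohort 4 (500/28 = 375/21 = 17.9 mg), so 20% of 15 would give 3 patients. That figure does not measure this problem. It counts any reported rise in patients of all kinds on monotherapy, and the events were generally low-grade. Among this trial's 133 MGA271 plus pembrolizumab patients, no bilirubin event is listed among treatment-related AEs at 5% or more (2.3.1.1.2).

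**Conclusion.** The point holds for 6.5.2.2.2. When a Gilbert's patient's usual bilirubin exceeds Grade 1 and a rise to no more than 3x ULN is managed as Grade 2, recovery to baseline does not meet the release test, and the text leads to discontinuation with oral steroids at 14 days. For 4.5.1 the finding is ambiguity only, for rises judged unrelated or not a DLT.

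The result rests on the assumed Grade 1 ceiling (1.5x to 2x ULN) and on baselines above it, which 10d allows but the documents do not count. The number affected is unknown, low and possibly zero. No primary objective or planned analysis is shown to be affected. It is worth correcting because the written consequence for an affected patient is substantial and the correction is small: a cheap improvement.

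**What to change.** For patients enrolled under the Gilbert's exception only:

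- In 6.5.2.2.2, change the Grade 2 hold line and the 14-day line to *Grade 1 or lower, or baseline, provided direct bilirubin is within normal limits*.
- In 4.5.1, add a conforming clarification to the restart condition.
- Use the baseline already defined in Protocol 9.1, the closest value before the initial dose.

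Leave unchanged the 3x ULN DLT and stop thresholds and the Hy's law, AST/ALT and hemolysis rules.

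The cost is one phrase in three places at the next amendment. Total and direct bilirubin are already in the special chemistry panel, so no new test is needed. The downside is that a few patients may restart with total bilirubin above Grade 1, judged against a single pre-dose value. The direct-bilirubin condition repeats the one used to admit them, and the unchanged thresholds still apply, which matters because bilirubin increase is a reported MGA012 event.
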